4.1.2 Forced Randomization

Not applicable.

4.2 Blinding and Unblinding

For details please refer to [section 3.3 'Blinding Procedure' of the protocol](#).

If a subject is unblinded during the study, it is to be reported as CSR-reportable PD (PD code 130), except for subjects unblinded by Pharmacovigilance due to suspected unexpected serious adverse reactions (SUSAR). The unblinding will be documented appropriately.

The unblinded subject(s) are excluded from the PPS. The unblinded subjects will be included in the FAS and safety sets.

Further details on measures taken to ensure blinding can be found in the study-specific Data Security Plan.

5. SAMPLE SIZE AND POWER CONSIDERATIONS

For details please refer to [section 8.5 'Sample Size and Power Considerations of Primary Objectives' of the protocol](#).

Sample size/power considerations are included in the study protocol.

6. DETERMINATION OF PROTOCOL DEVIATIONS

6.1 Definition of Protocol Deviations

CSR reportable PD are defined in accordance with ICH E3 as important PDs related to study inclusion or exclusion criteria, conduct of the trial, subject management or subject assessment resulting in the potential to jeopardize the safety or rights of the trial subjects or the scientific value of the trial.

All reportable PDs will be evaluated before unblinding and classified according to ICH into the following five categories:

- Subject developed withdrawal criteria during the study but was not withdrawn
 - Underlying medical condition forbidden by the protocol or which may influence immune response (PD code 240).
 - Subject had contraindication for a subsequent study vaccination but was vaccinated (PD code 220).
 - Concomitant infection related to the vaccine which may influence immune response (PD code 250).
- Subject received wrong vaccine or incorrect dose
 - Study vaccine was not administered at all (PD code 100)
 - Vaccine administration not according to protocol (PD code 140).
 - Randomization failure (vaccination not according to randomization) (PD code 120).
- Subject took an excluded concomitant medication
 - Administration of concomitant vaccine(s) forbidden in the protocol (PD code 150).
 - Administration of any medication forbidden by the protocol (PD code 230).
- Subject randomized and did not satisfy the entry criteria
 - Subject did not meet entry criteria (PD code 200).
- Deviation from key study procedures
 - Randomization code was broken (PD code 130).
 - Subject did not comply with study vaccination schedule (PD code 140.x).

- Subject did not provide any post-vaccination unsolicited safety data (PD code 115).
- Subject did not provide any post-vaccination solicited safety data (PD code 116).
- Subject did not comply with blood draw schedule (PD code 270).
- Serological results not available post-vaccination (PD code 110).
- Obvious incoherence, abnormal serology evolution or error in data (PD code 112).

CSR reportable PDs will lead to exclusion of the subject or part of the subject's data from at least one analysis set.

The number of subjects in any and by PD category will be summarized by vaccine, and overall. Individual subject listings will be provided in an appendix, sorted by subject and by PD category.

Prior to unblinding, designated GVGH staff will develop a memo that describes the PDs that led to exclusions from analysis sets. This memo will be signed off by at least the Biostatistician and the Physician and will be included in the trial master file (Exclusion Memo).

Prematurely terminating study participation for reasons such as withdrawal of consent or occurrence of adverse events (including death) is not considered as a PD. The missing assessments that should have otherwise been collected for that subject later in the study are also not considered as a PD.

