7.4 Per Protocol Set (PPS), Immunogenicity Set

All subjects in the FAS Immunogenicity who:

- Correctly receive the vaccine (i.e., receive the vaccine to which the subjects is randomized and at the scheduled time points).
- Have no CSR-reportable PD leading to exclusion (see [section 6.2](#)) as defined prior to unblinding.
- Are not excluded due to other reasons defined prior to unblinding (see [section 6.2](#))

In case of vaccination error, the subject is excluded from the PPS. If a subject receives a vaccine, labelled for another subject but the same as the one the subject was randomized to, the subject will not be removed from the PPS.

If a subject received the correct study vaccine (dose, batch) but from another ongoing study at the site, then the subject should be excluded from the PPS.

If a subject is unblinded during the study (except for SUSAR), he/she will be excluded from the PPS.

Summary tables will display the number of subjects available in the different analyses sets.

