7.7 Overview of Analysis Sets by PD Code

Table 7.7-1: Safety Sets

PD code	PD Description	Study Objective/ Period	All Exposed Set	Overall Safety Set	Safety Set, Unsolicited AEs, All study period	Safety Set, Solicited AEs, Period 1, T30-D7	Safety Set, Solicited AEs, Period 2, T30-D7
			Exclusion code	EXPFL	SAFFL	SSU10FL	SSS10FL
100	Study vaccine not administered AT ALL	All Study	EXC	EXC	EXC	EXC	EXC
115	Subject did not provide any post-vaccination unsolicited safety data – All study period	All Study			EXC		
116	Subject did not provide any post-vaccination solicited safety data	All Study				EXC	EXC
116.1	Subject did not provide any post-vaccination solicited safety data after 1st vaccination	Period 1				EXC	
116.2	Subject did not provide any post-vaccination solicited safety data after 2nd vaccination	Period 2					EXC

EXC = excluded from this analysis set.

Table 7.7-2: Immunogenicity Sets

PD code	PD Description	Study Objective/ Period	All Exposed	FAS 1 - day 28 after 1 st vac	FAS 2 - day 28 after 2 nd vac	PPS X -	PPS 1 - day 28 after 1 st vac	PPS 2 - day 28 after 2 nd vac	
				Exclusion code	EXPFL	FAS10FL	FAS20FL	PPSX0FL	PPS10FL
100	Study vaccine not administered AT ALL	All Study	EXC	EXC	EXC	EXC	EXC	EXC	EXC
110	Serological results are not available	All Study		EXC	EXC	EXC	EXC	EXC	EXC
110.3	Serological results are not available for visit 3 (post 1 st vac)	Visit 3		EXC		EXC	EXC		
110.5	Serological results are not available for visit 5 (post 2 nd vac)	Visit 5			EXC			EXC	
112	Obvious deviation from Laboratory Manual or error in laboratory data								
112.3	Incoherence between CRF and CLS database in terms of sample availability at visit 3	Visit 3				EXC	EXC		

PD code	PD Description	Study Objective / Period	All Exposed	FAS 1 - day 28 after 1 st vac	FAS 2 - day 28 after 2 nd vac	PPS X -	PPS 1 - day 28 after 1 st vac	PPS 2 - day 28 after 2 nd vac
				EXPF	FAS10FL			
112.5	Incoherence between CRF and CLS database in terms of sample availability at visit 5	Visit 5						EXC
120	Randomization failure		EXC	EXC	EXC	EXC	EXC	EXC
120.2	Subject received another vaccine than allocated (Actual Arm different from Planned Arm) at 1 st vacc	All study		EXC	EXC	EXC	EXC	EXC
130	Randomization code was broken	All study				EXC	EXC	EXC
140	Vaccination not according to protocol					EXC	EXC	EXC
140.1	Administration of temperature-deviated vaccine					EXC	EXC	EXC

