11.3 Secondary Objectives Analysis

Secondary Objective:

To evaluate the immunogenicity profile of two injections of *S. sonnei* 1790GAHB vaccine in healthy adults by measuring the anti-LPS *S. sonnei* serum IgG.

The measures of the immunogenicity outcome, (i.e., the anti-LPS *S. sonnei* serum IgG), will include:

- a. IgG geometric mean concentrations (GMCs) pre-vaccination (Day 1), 28 days after 1st vaccination and 28 days after 2nd vaccination, as determined by Enzyme-linked Immunosorbent Assay (ELISA), and applicable geometric mean ratios between post- and pre-vaccination samples.
- b. Number and percentage of subjects with seroresponse for anti- LPS *S. sonnei* at 28 days after 1st vaccination and 28 days after 2nd vaccination

Seroresponse is aimed to define a significant increase in post vaccination samples based on the biological performance of this specific serology assay and it is defined as:

- If the baseline value is greater than 50 ELISA Units (EU) then an increase of at least 50% in the post-vaccination sample as compared to baseline [i.e. $((\text{Post-vac} - \text{baseline})/\text{baseline})100\% \geq 50\%$]
- If the baseline value is less or equal to 50 EU then an increase of at least 25 EU in the post-vaccination sample as compared to baseline [i.e. $(\text{post-vac} - \text{baseline}) \geq 25 \text{ EU}$]
- c. Number and percentage of subjects with titers post vaccination concentration ≥ 121 for anti-LPS *S. sonnei* at 28 days after 1st vaccination and 28 days after 2nd vaccination
- d. IgG GMCs pre-vaccination (Day 1), 28 days after 1st vaccination and 28 days after 2nd vaccination by antibody titer at baseline (i.e., above vs. below the assay detection limit), as determined by ELISA, and applicable geometric mean ratios between post- and pre-vaccination samples.
- e. Number and percentage of subjects with seroresponse for anti- LPS *S. sonnei* at 28 days after 1st vaccination and 28 days after 2nd vaccination by antibody titer at baseline (i.e., above vs. below the assay detection limit)

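### SAP 6.1 makes an abnormal antibody course a reportable deviation that must lead to exclusion, while Table 7.7-2 limits the same code to laboratory and sample problems

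*SAP*

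**What the plan says.** SAP 6.1 lists the reportable deviations. Under departures from key study procedures it includes "Obvious incoherence, abnormal serology evolution or error in data (PD code 112"). It then states the consequence for the whole list: "CSR reportable PDs will lead to exclusion of the subject or part of the subject's data from at least one analysis set".

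SAP 7.4 puts this into effect for the per protocol set (PPS), whose members must "Have no CSR-reportable PD leading to exclusion".

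SAP Table 7.7-2, which assigns deviation codes to immunogenicity sets, describes code 112 differently, as "Obvious deviation from Laboratory Manual or error in laboratory data". That parent row carries no exclusion mark in any column. The table has two sub-codes under it:

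- 112.3: "Incoherence between CRF and CLS database in terms of sample availability at visit 3", marked as excluded from PPS X and PPS 1.
- 112.5: "Incoherence between CRF and CLS database in terms of sample availability at visit 5", marked as excluded from PPS 2.

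On timing, SAP 6.1 says: "All reportable PDs will be evaluated before unblinding and classified according to ICH into the following five categories".

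**The concern.** The serology in question is the outcome. SAP 11.3 introduces the secondary endpoints with "The measures of the immunogenicity outcome, (i.e., the anti-LPS *S. sonnei* serum IgG), will include", followed by geometric mean concentrations (GMCs), within-subject ratios (GMRs), seroresponse and the proportion reaching 121 units. How a subject's serology evolves from baseline to visits 3 and 5 is what those endpoints measure. A rule that treats an abnormal evolution as a deviation, separately from any data error, lets a subject be removed because of the result.

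Neither document gives a threshold, a pattern or an example of abnormality. A flat course, a decline, or a rise from natural exposure could each be called abnormal, and a different reviewer could decide otherwise. If valid values were removed on that basis, GMC, GMR and seroresponse in the affected set would describe a group selected on its own results. The assumption in SAP 8.2.2 and 11.3 that missing immunogenicity values are missing completely at random would be false for values deleted because of their level.

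**Working it through.** The plan states no figure on this point, so the check is mainly a comparison of text.

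**1. Is the serology limb distinct from error?** In 6.1 it stands beside incoherence and error in data as one of three alternatives. Other legitimate causes of an odd course have their own codes in the same list: vaccine-related concomitant infection (250), a forbidden vaccine (150), a forbidden medication (230) and unavailable results (110). Read literally, the limb adds exclusion for the antibody course alone.

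**2. Does the table carry it?** No. Table 7.7-2 covers laboratory-manual departures, laboratory data errors and sample-availability mismatches. No row covers the shape of a titre course. So 6.1 requires an exclusion for which the table names no set.

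**3. Which sets could be affected?**

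| Source | Deviation criterion? |
|---|---|
| SAP 7.3, FAS | None: randomized, at least one vaccination, data at the time point |
| SAP 7.6, modified FAS | None: changes only the grouping of wrong-vaccine subjects |
| Protocol 8.3.6, modified FAS | None for serology: regroups wrong-vaccine subjects and excludes later visits after a missed vaccination |
| SAP 7.4, PPS | Yes: no reportable deviation leading to exclusion |
| Table 7.7-2, 112.3 and 112.5 | PPS columns only |
| Table 7.7-2, parent row 112 | No set marked |
| Table 7.7-2, modified FAS | No such column |
| SAP 6.1 | At least one set, not named |
| Protocol 8.3.8 | Reportable deviations are exclusionary from the analysis; not limited to the PPS |

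The PPS is the natural destination. The modified FAS is protected by its definition, but no sentence says that code 112 stops at the PPS.

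**4. Which estimates use those sets?** Protocol 8.4.3.3.2 and SAP 8.2.2 place the immunogenicity objective on the modified FAS. Protocol 8.3.5 requires the PPS to be defined even where no objective needs it. The SAP text describes no PPS estimate of GMC, GMR or seroresponse. The full list of tables is in a separate table of contents (SAP 17) that is not among the documents, so a supportive PPS table can be neither confirmed nor excluded.

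**5. Illustration only.** The one input from the documents is 20 evaluable subjects per group (protocol synopsis). Responder counts and numbers removed are assumed. With x responders and k non-responders removed, the rate is x/(20 − k).

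| Assumed responders | k = 0 | k = 1 | k = 2 |
|---|---|---|---|
| 10 | 50.0% | 52.6% | 55.6% |
| 14 | 70.0% | 73.7% | 77.8% |
| 16 | 80.0% | 84.2% | 88.9% |
| 18 | 90.0% | 94.7% | 100% |

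Each removed non-responder adds about 3 to 5 points. For 14 responders the Clopper-Pearson 95% interval moves from 45.7–88.1% (14/20) to 52.4–93.6% (14/18). The direction depends on who is removed: taking out 2 responders instead gives 12/18 = 66.7%.

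**The case against.** The strongest defence is that no described analysis is affected. The FAS and modified FAS have no deviation criterion, the sub-codes of 112 exclude only from PPS columns, a PPS exclusion satisfies 6.1, and the objective is analysed on the modified FAS. Most of this stands, and it is why a bias in the primary immunogenicity analysis cannot be claimed. It is not complete. The parent row assigns no set, 6.1 allows part of a subject's data to be dropped, and FAS membership itself depends on having data at the visit. Nor can the table settle the matter alone. It marks sub-code 120.2 (wrong vaccine at the first vaccination) as excluded from both FAS sets, whereas SAP 4.1.1 and 7.3 keep such subjects in the FAS as randomized.

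A second defence is that the phrase, placed between incoherence and error, means a pattern suggesting a swapped sample or assay fault. That is plausible and may be the intent, but the words do not say it.

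A third is procedural. Deviations are judged before unblinding, on blinded data (SAP 6.1, 6.2), and recorded in a memo signed by at least the biostatistician and the physician. They are summarized by vaccine and listed by subject, and the assay is run blind to arm and visit (protocol 7.3). These steps make exclusions visible and limit abuse. They do not prevent selection on the outcome, because an odd course can be seen without the group code.

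A reader might go further and infer that the sponsor means to remove non-responders, or that reviewing the curves breaks the blind. The documents do not support either. They nowhere call non-response, decline or natural boosting abnormal, and how far a course reveals the arm is unquantified.

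**Conclusion.** The point holds as a conflict between SAP 6.1 and Table 7.7-2 that leaves outcome-dependent exclusion from the per protocol sets open. The primary immunogenicity analysis on the modified FAS is probably unaffected. That rests on the set definitions overriding the general exclusion sentence in 6.1, which is the better reading but is not written down.

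The size is unknown. A reader might take the move from 70.0% to 77.8% as an expected bias in the trial's seroresponse rate. It is not: the 14 responders and 2 exclusions are assumptions, and on the better reading the shift in the modified FAS is zero. The trial is descriptive and has no hypothesis or success criterion, so no formal conclusion turns on this. It should still be corrected, because the correction costs little and the rule as worded selects on the endpoint.

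**What to change.** In SAP 6.1, delete the words *abnormal serology evolution* and give code 112 the same meaning as in Table 7.7-2. Then add three statements:

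1. An implausible titre may trigger a check of sample identity or of the assay.
2. Data are excluded under code 112 only if that check documents a sample or laboratory error.
3. An unusual antibody course alone never removes a subject or a value from the FAS, modified FAS or PPS.

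Mark in Table 7.7-2 which sets the parent row of code 112 affects. Make the change before the Exclusion Memo is signed.

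The cost is a few lines of SAP text, with no new data and no change to study procedures. The downside is that odd but valid values stay in the analysis, including the PPS. With about 20 subjects per group, one extreme titre can move a GMC. It can be pointed out in the listings without being removed.

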6.2 Determination of Protocol Deviations

All protocol deviations will be tracked by using the protocol deviations log according to GVGH SOP MON2403. Protocol deviations will be provided to the GVGH Project Physician (PP) and GVGH Head of Clinical Operations (HCO) for review, on an ongoing basis during the study.

GVGH Project Physician, Clinical Research Associate (CRA) and HCO will provide the Biostatistician with:

- An assessment of CSR reportable PDs based on blinded clinical data review.
- An assessment of subjects without PDs (e.g., premature withdrawals due to adverse event, withdrawal of consent) who should be excluded from an analysis set.

6.3 Exclusions of Individual Values for Safety Analysis

Some local and systemic adverse events will be directly measured by the subject and will not be subject to a reconciliation process, even if they are biologically implausible. Therefore these implausible measurements will be removed from the analysis but included in listings. Implausible measurements are summarized in the table below:

Table 6.3-1: Implausible Solicited Adverse Events

Parameter	Implausible measurements
Body temperature	$\leq 33^{\circ}\text{C}$ or $\geq 42^{\circ}\text{C}$
Erythema	For subjects ≥ 6 years: ≥ 900 mm Measurements < 0 mm
Induration	For subjects ≥ 6 years: ≥ 500 mm Measurements < 0 mm

7. ANALYSIS SETS

7.1 All Enrolled Set

All screened subjects who provide informed consent and provide demographic and/or other baseline screening measurements, regardless of the subject's randomization and vaccination status in the trial, and receive a subject ID (starting with 01).

Demography and baseline characteristics tables as well as subject listings will be produced on the All Enrolled Set.

7.2 Exposed Set

All subjects in the All Enrolled Set who receive a study vaccination.

7.3 Full Analysis Set (FAS), Immunogenicity Set

All subjects in the All Enrolled Set who are randomized, receive at least one study vaccination and provide immunogenicity data at relevant time points.

- Received at least one study vaccination and provide immunogenicity data 28 days after 1st vaccination. (FAS 1 - day 28 after 1st vac)
- Received at least one study vaccination and provide immunogenicity data 28 days after 2nd vaccination. (FAS 2 - day 28 after 2nd vac)

In case of vaccination error, subjects in the FAS will be analyzed “as randomized” (i.e., according to the vaccine a subject was designated to receive, which may be different from the vaccine the subject actually received).

If a subject is unblinded during the study, he/she will be included in the FAS.

7.4 Per Protocol Set (PPS), Immunogenicity Set

All subjects in the FAS Immunogenicity who:

- Correctly receive the vaccine (i.e., receive the vaccine to which the subjects is randomized and at the scheduled time points).
- Have no CSR-reportable PD leading to exclusion (see [section 6.2](#)) as defined prior to unblinding.
- Are not excluded due to other reasons defined prior to unblinding (see [section 6.2](#))

In case of vaccination error, the subject is excluded from the PPS. If a subject receives a vaccine, labelled for another subject but the same as the one the subject was randomized to, the subject will not be removed from the PPS.

If a subject received the correct study vaccine (dose, batch) but from another ongoing study at the site, then the subject should be excluded from the PPS.

If a subject is unblinded during the study (except for SUSAR), he/she will be excluded from the PPS.

Summary tables will display the number of subjects available in the different analyses sets.

7.5 Safety Set

Solicited Safety Set

All subjects in the Exposed Set with any solicited adverse event data and/or indicators of solicited adverse events (e.g., use of analgesics/antipyretics)].

For the by vaccination tabulations, solicited safety sets will be defined as follows:

- Solicited safety set #1 for post-injection reactions after the first dose (SOL 1)
- Solicited safety set #2 for post-injection reactions after the second dose (SOL 2)

Unsolicited Safety Set

All subjects in the Exposed Set with unsolicited adverse event data.

In this respect, a confirmation of no AE is considered as adverse event data; hence subject is to be included.

Overall Safety Set

All subjects who are in the solicited safety set and/or in the unsolicited safety set.

In case of vaccination error, subjects will be analyzed as “treated” (i.e., according to the vaccine a subject receives, rather than the vaccine to which the subject is randomized).

If a subject received the correct study vaccine (dose, batch) but from another ongoing study at the site then the subject’s safety data should be included in the safety analysis.

If a subject is unblinded during the study, he/she will be included in all the safety sets.

7.5.1 Restricted Safety Set

Not applicable.

7.6 Other Analysis Set

Modified FAS

The difference between FAS and Modified FAS are:

Subjects who received a wrong vaccine at both vaccinations will be analyzed in the vaccine the subject actually received (in the FAS they will be analyzed according to the vaccine the subject was designed to receive)

7.7 Overview of Analysis Sets by PD Code

Table 7.7-1: Safety Sets

PD code	PD Description	Study Objective/ Period	All Exposed Set	Overall Safety Set	Safety Set, Unsolicited AEs, All study period	Safety Set, Solicited AEs, Period 1, T30-D7	Safety Set, Solicited AEs, Period 2, T30-D7
			Exclusion code	EXPFL	SAFFL	SSU10FL	SSS10FL
100	Study vaccine not administered AT ALL	All Study	EXC	EXC	EXC	EXC	EXC
115	Subject did not provide any post-vaccination unsolicited safety data – All study period	All Study			EXC		
116	Subject did not provide any post-vaccination solicited safety data	All Study				EXC	EXC
116.1	Subject did not provide any post-vaccination solicited safety data after 1st vaccination	Period 1				EXC	
116.2	Subject did not provide any post-vaccination solicited safety data after 2nd vaccination	Period 2					EXC

EXC = excluded from this analysis set.

Table 7.7-2: Immunogenicity Sets

PD code	PD Description	Study Objective/ Period	All Exposed	FAS 1 - day 28 after 1 st vac	FAS 2 - day 28 after 2 nd vac	PPS X -	PPS 1 - day 28 after 1 st vac	PPS 2 - day 28 after 2 nd vac	
				Exclusion code	EXPFL	FAS10FL	FAS20FL	PPSX0FL	PPS10FL
100	Study vaccine not administered AT ALL	All Study	EXC	EXC	EXC	EXC	EXC	EXC	EXC
110	Serological results are not available	All Study		EXC	EXC	EXC	EXC	EXC	EXC
110.3	Serological results are not available for visit 3 (post 1 st vac)	Visit 3		EXC		EXC	EXC		
110.5	Serological results are not available for visit 5 (post 2 nd vac)	Visit 5			EXC			EXC	
112	Obvious deviation from Laboratory Manual or error in laboratory data								
112.3	Incoherence between CRF and CLS database in terms of sample availability at visit 3	Visit 3				EXC	EXC		

PD code	PD Description	Study Objective / Period	All Exposed	FAS 1 - day 28 after 1 st vac	FAS 2 - day 28 after 2 nd vac	PPS X -	PPS 1 - day 28 after 1 st vac	PPS 2 - day 28 after 2 nd vac
				EXPF	FAS10FL			
112.5	Incoherence between CRF and CLS database in terms of sample availability at visit 5	Visit 5						EXC
120	Randomization failure		EXC	EXC	EXC	EXC	EXC	EXC
120.2	Subject received another vaccine than allocated (Actual Arm different from Planned Arm) at 1 st vacc	All study		EXC	EXC	EXC	EXC	EXC
130	Randomization code was broken	All study				EXC	EXC	EXC
140	Vaccination not according to protocol					EXC	EXC	EXC
140.1	Administration of temperature-deviated vaccine					EXC	EXC	EXC

PD code	PD Description	Study Objective / Period	All Exposed	FAS 1 - day 28 after 1 st vac	FAS 2 - day 28 after 2 nd vac	PPS X -	PPS 1 - day 28 after 1 st vac	PPS 2 - day 28 after 2 nd vac
				EXPF	FAS10FL			
140.2	Administration of expired vaccine					EXC	EXC	EXC
140.5	Incomplete vaccination series					EXC	EXC	EXC
150	Administration of forbidden vaccine between Visit X and Visit Y	Visit X – Visit Y				EXC		
200	Subject did not meet entry criteria	All study				EXC	EXC	EXC
260	Did not comply with study vaccination schedule					EXC		
260.2	2 nd vaccination not done or performed out of planned visit window							EXC
270	Did not comply with blood draw schedule							

PD code	PD Description	Study Objective / Period	All Exposed	FAS 1 - day 28 after 1 st vac	FAS 2 - day 28 after 2 nd vac	PPS X -	PPS 1 - day 28 after 1 st vac	PPS 2 - day 28 after 2 nd vac
				EXPF	FAS10FL		PPS10FL	PPS20FL
270.3	Blood draw at visit 3 not done or performed out of planned visit window	Visit 3					EXC	
270.5	Blood draw at visit 5 not done or performed out of planned visit window	Visit 5						EXC

FAS = Full Analysis Set; PPS=Per Protocol Set; M=Month EXC = excluded from this analysis set.

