4.1.1 Definition of Randomization/Vaccination Errors

The list below provides some examples of potential errors that may occur during vaccination:

- Subjects got vaccinated with a vaccine different from the one assigned at randomization (PD code 120)
- Subjects got vaccinated with the correct vaccine but containing a lower volume (PD code 140.3)
- Subjects got vaccinated by route of administration different from the one assigned at randomization

Differentiate between incorrect stratification and misrandomizations.

A misrandomization is defined as a subject receiving a vaccine other than the one assigned by randomization. Misrandomization is a Clinical Study Report (CSR)-reportable Protocol Deviation (PD) and should be analyzed as randomized in Full Analysis Set (FAS), excluded from Per Protocol Set (PPS) and analyzed as received for Safety.

Incorrect stratification is defined as enrollment and randomization of a subject based on incorrect stratification information at baseline. Incorrect stratifications should be split for major and minor errors.

- Major stratification errors: resulting in administration of incorrect dosage or schedule, not corrected on time, i.e. not corrected before administration of the vaccine. These will be handled as CSR-reportable PD.
- Minor stratification errors: not having impact on dose/schedule administered. These will *not* be considered as CSR reportable PD.

Stratification error	FAS	PPS	Safety Set
Minor	Analyze as corrected	Analyze as corrected	Analyze as corrected
Major	Analyze as originally stratified	Exclude from analysis	Analyze as corrected

Please see [section 7](#) of this document for a complete guidance on how vaccination errors are handled in the statistical analysis.

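### SAP Table 7.7-2 excludes PD code 120 (wrong vaccine given) from the All Exposed Set, against the SAP's own definitions; if the flag is built from that row, some vaccinated subjects leave the safety summaries

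*SAP*

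**What the plan says.** SAP 7.7 sets out, by protocol-deviation code, which subjects leave which analysis set. Table 7.7-2 covers the immunogenicity sets and includes an All Exposed column. Its code 120 row is labelled "Randomization failure", has a blank period cell, and then EXC under All Exposed, FAS 1, FAS 2, PPS X, PPS 1 and PPS 2. SAP 4.1.1 and 6.1 both give the meaning of code 120: the subject was vaccinated, but not with the vaccine assigned by randomization.

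The next row, sub-code 120.2, is described as "Subject received another vaccine than allocated (Actual Arm different from Planned Arm) at 1 st vacc". It leaves All Exposed blank and puts EXC in the other five columns. Table 7.7-1, which covers the safety sets, has its own All Exposed column; only code 100 (no study vaccine at all) is EXC there, and code 120 does not appear.

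The SAP text says:
- SAP 7.2, Exposed Set: "All subjects in the All Enrolled Set who receive a study vaccination".
- SAP 7.5, Unsolicited Safety Set: "All subjects in the Exposed Set with unsolicited adverse event data". The Solicited Safety Set is drawn from the Exposed Set in the same way, and the Overall Safety Set is the union of the two.
- SAP 7.5, vaccination errors: analysed "according to the vaccine a subject receives, rather than the vaccine to which the subject is randomized".
- SAP 4.1.1, misrandomization: "excluded from Per Protocol Set (PPS) and analyzed as received for Safety".

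**The concern.** Safety is the primary objective, and the Exposed Set is the parent of every safety set. A subject who received the wrong product or dose level has been exposed to a study vaccine. If the table removes that subject from the Exposed Set, the as-treated rule has nothing to act on for that subject, and any reaction, laboratory deviation, SAE or AESI leaves both numerator and denominator of the summaries built on those sets. With 24 subjects planned per arm, one subject is 1/24 = 4.2 percentage points of an arm.

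The two tables also give different rules for one flag. Both headers name the exposed flag EXPFL, and the SAP does not say which table takes precedence. SAP 4.1.1 sends the reader to section 7 for the handling of vaccination errors in the analysis, and the only code 120 rows in that section's tables are in Table 7.7-2.

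**Working it through.** **1. Does the EXC really sit under All Exposed?** The relevant part of Table 7.7-2 has nine columns: code, description, period, and six sets.

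| Row | Period | All Exposed | FAS 1 | FAS 2 | PPS X | PPS 1 | PPS 2 |
|---|---|---|---|---|---|---|---|
| 120 | blank | EXC | EXC | EXC | EXC | EXC | EXC |
| 120.2 | All study | blank | EXC | EXC | EXC | EXC | EXC |
| 130 | All study | blank | blank | blank | EXC | EXC | EXC |
| 140 | blank | blank | blank | blank | EXC | EXC | EXC |

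All four rows fill exactly nine cells, so a column shift in row 120 is not apparent. Row 120 is also not just a heading: parent rows 112 and 270 carry no EXC, while row 120 carries six.

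**2. Is a code 120 subject exposed?**

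| Source | Status of a subject given the wrong vaccine |
|---|---|
| SAP 7.2 | In the Exposed Set |
| SAP 4.1.1, 7.5 | In the safety analysis, under the vaccine received |
| Table 7.7-1 | Not excluded from All Exposed or any safety set |
| Table 7.7-2, code 120.2 | Not excluded from All Exposed |
| Table 7.7-2, code 120 | Excluded from All Exposed |

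The last line stands alone against the other four.

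**3. Who would be lost if the flag followed the code 120 row?** Sub-code 120.2 covers a wrong vaccine at the first vaccination, and a subject carried under it stays exposed. No sub-code is listed for a wrong vaccine at the second vaccination only, so that subject would be coded at parent level, which is the level SAP 4.1.1 and 6.1 themselves use. Those are the subjects at risk.

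**4. Which outputs would be affected?** Summaries on the Solicited, Unsolicited and Overall Safety Sets, including the laboratory summaries (SAP 13.5 uses the Overall Safety Set). The exposure table (SAP 13.1) and the subject listings (SAP 7.1) use the All Enrolled Set and would not change.

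**5. Size.** The plan gives no figure for this point. Its one safety calculation, in the protocol synopsis, is the chance of at least one event among 20 evaluable subjects at a true rate of 10%, stated as 87%. It reproduces: 1 − 0.9^20 = 0.878. Losing one subject gives 1 − 0.9^19 = 0.865. From 24 subjects, 1 − 0.9^24 = 0.920 becomes 1 − 0.9^23 = 0.911. The loss of detection probability is about one percentage point.

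The larger effect arises if the lost subject has the event. Assume one such subject with the only event in an as-treated group of 24 (Clopper-Pearson 95% intervals):
- kept: 1/24 = 4.2% (0.1% to 21.1%)
- dropped: 0/23 = 0% (0% to 14.8%)

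If an unbalanced error makes the as-treated group 25, the change is from 1/25 = 4.0% (0.1% to 20.4%) to 0/24 = 0% (0% to 14.2%).

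**The case against.** The strongest reply is that Table 7.7-1 is the table for the safety sets. It has its own All Exposed column and does not exclude code 120, and the text of SAP 4.1.1, 7.2 and 7.5 agrees with it. A programmer who follows the safety table and the text loses nobody. This stands, and it makes the consequence conditional. It does not remove the contradiction, since both tables name the same flag and neither is given precedence.

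A reader might infer that the SAP drops every wrongly vaccinated subject from all primary safety tables, or that the as-treated rule can never operate. The documents do not support this. Table 7.7-1 keeps these subjects, sub-code 120.2 keeps those with a wrong first vaccine, and the exposure table and listings use the All Enrolled Set. An SAE would still be listed: protocol 8.4.2.1.3 requires by-subject listings of all adverse events.

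Two further objections carry some weight. First, the table text was machine-read from a PDF, and another part of it is visibly displaced (row 100 shows seven EXC entries for six sets). Row 120 agrees with its neighbours, but the cell should be confirmed in the source document. Second, protocol 5.1.4 uses the same label for a subject who was enrolled but never randomized, for whom exclusion from the Exposed Set would be natural. SAP 6.1, however, defines code 120 as vaccination not according to randomization, and code 100 already covers subjects given no vaccine.

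**Conclusion.** The All Exposed entry for code 120 is wrong as written: it contradicts SAP 7.2, SAP 4.1.1 and 7.5, Table 7.7-1, and its own sub-code. The practical risk is small and conditional. It arises only if the exposed flag is programmed from that row, and then only for subjects coded solely at parent level 120. The documents give no expected number of such subjects, and it may be zero. The change from 1/24 to 0/23 is an illustration under the assumptions stated, not a prediction. The conclusion rests on the row reading in the source document as it does in the extracted text, and on subjects coded 120.2 not also being carried at parent level. It is worth correcting because it concerns the population for the primary objective.

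**What to change.** In Table 7.7-2, clear the All Exposed cell for code 120 so that it matches sub-code 120.2. In Table 7.7-1, add a row or footnote stating that codes 120 and 120.x stay in the Exposed and Safety Sets under the vaccine actually received. A sub-code for a wrong vaccine at the second vaccination would close the gap that leaves such subjects at parent level.

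The cost is one cell, one note and, if adopted, one extra code in the SAP, plus one flag rule in programming. No data collection, sample size or stated figure changes.

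While these rows are open, a separate conflict can be settled: codes 120 and 120.2 are both EXC from FAS 1 and FAS 2, whereas SAP 4.1.1 and 7.3 keep such subjects in the FAS as randomized.
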